7.4.3 Continuous outcomes measured at single time points

Continuous outcome variables measured at single time points will be analysed with two-sample t-tests (and 95% confidence intervals for the differences between means), with adjustment for unequal variances (the Welch U test). In situations where the distribution of the variable is difficult to assess or deemed to be highly skewed, median regression models will be used instead of t-tests to test and estimate differences in medians.

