2.1.3 CMT pain trial

This trial will include 40 patients from the pilot trial and the first 40 patients from the CMT2-trial included at the birth clinic of OUH, Rikshospitalet.

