4.1.3 CMT pain trial

The primary endpoint is treatment difference in opioid consumption and reported pain intensity within the first 48h after test drug administration.

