6.2.4 Blood loss

Blood loss will be estimated by the formula for calculated blood loss as published by Stafford, revised with weight in kg and height in cm(7).

A continuous variable measured in mL.

6.2.5 Perioperative side effects.

During the first 10 minutes after administration of test drug, the patient will be asked to report any side effects. Severity of side effects will be registered in time gaps as follows 0-2 min, 2-5 min and 5-10 min.

Severity of side effects is an ordered categorical variable:

- 0 = no side effects at the given point
- 1 = mild side effects
- 2 = moderate side effects
- 3 = severe side effects.

Treatment given to alleviate side effects (a binary variable) will be registered as

- 0 = no treatment administered
- 1 = treatment administered

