6.2.7 Consumption of analgesics

Postoperative pain treatment protocol includes oral paracetamol 1 g and ibuprofen 400 mg 4 times daily and IV morphine administered by a patient controlled analgesia pump (PCA). In the CMT pain trial, overall postoperative morphine consumption in mg will be measured, as well as morphine consumption in the time periods 0-4h, 4-10h, 10-24h and 24-48h after test drug administration.

A continuous variable measured in mg.

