6.2.8 QOL forms detecting level of anxiety, depression and pain catastrophizing trait

Prior to the operation the patients will be asked to fill in QOL forms detecting level of anxiety, depression and pain catastrophizing trait. Only in the CMT pain trial.

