6.2.8.1 Modified three simple questions

A numeric rating scale ranging from 0-100 is used to rate anxiety, anticipated level of pain, need for analgesics and coping with motherhood (0 = not at all, 100 = to an extreme degree). The variables will be treated as continuous in the statistical analyses.

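### SAP 7.4.3 compares blood loss and overall 48-hour morphine without covariates: valid, but it forgoes precision available from pre-treatment data the trial already collects

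*SAP*

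**What the plan says.** - **Method.** SAP 7.4.3: "Continuous outcome variables measured at single time points will be analysed with two-sample t-tests", with adjustment for unequal variances. If the distribution is highly skewed or hard to judge, "median regression models will be used instead of t-tests to test and estimate differences in medians". No covariate is named in either branch.
- **Blood loss.** SAP 6.2.4 defines one calculated value per woman: "A continuous variable measured in mL". Protocol 6.2.2 shows that the formula uses pre-operative weight and height. The protocol synopsis lists blood loss as the efficacy criterion; Protocol 2.2 lists it as a secondary endpoint.
- **Morphine.** SAP 6.2.7: "overall postoperative morphine consumption in mg will be measured", alongside amounts in four time periods. SAP 4.1.3, for the pain trial: "The primary endpoint is treatment difference in opioid consumption and reported pain intensity within the first 48h after test drug administration".
- **Pain-trial sample.** SAP 2.1.3: "This trial will include 40 patients from the pilot trial and the first 40 patients from the CMT2-trial", the latter from Rikshospitalet.
- **Pre-treatment data.** SAP 6.2.8: "Prior to the operation the patients will be asked to fill in QOL forms detecting level of anxiety, depression and pain catastrophizing trait". SAP 6.2.8.1: "A numeric rating scale ranging from 0-100 is used to rate anxiety, anticipated level of pain, need for analgesics and coping with motherhood". Weight, height, parity and gestation are recorded at baseline (Protocol 6.1), and haemoglobin at 0 h (SAP 2.3).
- **Stated use of the psychological scores.** SAP 3.2 plans only to describe how they relate to opioid use and pain. Protocol 6.2.1 calls the association with post-surgical pain a possibility to be assessed.

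**The concern.** The SAP adjusts for baseline wherever an outcome has a baseline of its own (7.4.2). Blood loss and total morphine have none, so they fall to 7.4.3 and lose all adjustment, although other pre-treatment variables that may predict them are on file.

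The pain trial has 80 women, so explainable between-woman variance widens the interval on its morphine total noticeably. It also pools two separately recruited cohorts: pilot inclusion ended in June 2018, and CMT2 was expected to start in January 2019. No cohort term is specified. For blood loss, weight and height enter the outcome's own formula, so some predictive value is built in. At stake is the width of two confidence intervals, not their validity.

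**Working it through.** **1. Which outcomes fall under 7.4.3.** The SAP assigns neither variable there by name. Blood loss and overall morphine are each one value per woman with no baseline of the same quantity, so 7.4.2 does not reach them and 7.4.3 does. Morphine by period (four values) and pain intensity (four times, SAP 6.2.6) are measured at more than two time points, and 7.4.5 sends those to mixed models.

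**2. The plan's own figure.** The only sample size with a calculation is for troponin I (SAP 7.1.2): difference 1.37, SDs 0.79 and 4.48, two-sided 5%, 80% power, unequal-variance t-test. At 89 per arm:
- SE = √[(0.79² + 4.48²)/89] = √(20.69/89) = 0.482
- Noncentrality = 1.37/0.482 = 2.84; Satterthwaite df = 93.5
- Power = 80.3% at 89 per arm and 79.8% at 88, so 89 × 2 = 178. Reproduced exactly.

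This number concerns troponin I, which 7.4.2 already adjusts for baseline, so nothing below changes it. No SD, target difference or sample size is given for morphine or blood loss, so results are in SD units.

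**3. Formula for the adjusted comparison.** With n per arm, p covariates and R² the share of outcome variance they explain:
- SE(difference) = SD × √[(1 − R²) × (2/n) × (1 + p/(2n − p − 3))]
- df = 2n − 2 − p; power from the noncentral t distribution.

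The last factor charges for chance imbalance in the covariates. R² is not in the documents; a range from 0 to 0.30 is assumed.

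**4. Overall morphine, about 40 per arm, p = 3.** The charge is 1 + 3/74 = 1.041.

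| | Detectable difference, 80% power (SD) | Power at 0.634 SD |
|---|---|---|
| Unadjusted | 0.634 | 80% |
| R² = 0 | 0.647 | 78.4% |
| R² = 0.05 | 0.631 | 80.4% |
| R² = 0.10 | 0.614 | 82.5% |
| R² = 0.20 | 0.579 | 86.6% |
| R² = 0.30 | 0.542 | 90.7% |

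Break-even is where (1 − R²) × 1.041 = 1, that is R² ≈ 0.04. Before the charge for covariates, 80/(1 − R²) gives the equivalent unadjusted sample: about 89, 100 and 114 women at R² 0.10, 0.20 and 0.30.

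A simulation (4,000 runs per R², normal outcomes, 40 per arm) agrees. Power at 0.634 SD, unadjusted against adjusted, was 80.2% and 82.0% at R² 0.10, 79.5% and 86.8% at 0.20, and 80.3% and 89.8% at 0.30. Type I error was 4.8-5.4% for both analyses.

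**5. Blood loss in CMT2, p = 4.** Evaluable numbers are bracketed by 89 per arm (the calculated minimum) and 120 per arm (240 enrolled, none lost).

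| | 89 per arm (SD) | 120 per arm (SD) |
|---|---|---|
| Unadjusted | 0.422 | 0.363 |
| R² = 0.10 | 0.405 | 0.347 |
| R² = 0.30 | 0.357 | 0.306 |

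The fix below uses three covariates for blood loss. Recomputing with p = 3 changes these adjusted values by at most 0.001 SD.

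**The case against.** The strongest reply is that nothing here is an error. A Welch test between randomised arms is unbiased and holds its type I error, and the simulation confirms it. Pooling pilot and CMT2 women brings no systematic bias either, since both cohorts are randomised 1:1. That stands in full.

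The reply is also right on these points:
- **Predictive value is not shown.** A reader might infer that the psychological scores are known predictors of opioid use. The documents treat this as an open question. If they predict nothing, adjustment costs 1-2 points of power.
- **Scope.** A reader might infer that the whole pain-trial primary endpoint goes unadjusted to a t-test. Only the overall morphine total does; pain intensity and period-wise morphine go to mixed models under 7.4.5.
- **The fallback.** Morphine and blood loss may well be skewed and end in median regression. The √(1 − R²) gain is derived for means and may not carry over in size.
- **Importance.** Blood loss is an efficacy criterion only in the synopsis. Protocol 10.3 names troponin I as the primary efficacy variable, and morphine is primary only in a substudy.
- **Cost.** The questionnaires can be incomplete, and a complete-case regression would drop women from a sample of 80.

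What the reply does not remove is that no section adjusts either comparison, the variables are already collected, and the possible loss from using a few of them is small and bounded.

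**Conclusion.** The point holds as a cheap improvement of lower severity. For overall morphine, the assumed R² range of 0 to 0.30 moves the detectable difference from 0.634 SD to between 0.647 and 0.542 SD, with gain once R² exceeds about 0.04. For blood loss, R² of 0.10 to 0.30 lowers it by 0.017 to 0.065 SD at 89 per arm (0.422 to 0.405 or 0.357) and by 0.016 to 0.057 SD at 120 per arm (0.363 to 0.347 or 0.306). Some gain is more plausible for blood loss, because weight and height are formula inputs. The part played by haemoglobin in the formula is an inference, since the formula itself is not reproduced in the documents.

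The calculation rests on the assumed R², roughly equal arms in the pain trial, and analysis on means. A reader might go further and conclude that the planned tests are biased or that the trial's main conclusion is weakened. The documents support neither: the tests are valid, and troponin I is already baseline-adjusted.

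**What to change.** Before unblinding, amend SAP 7.4.3 so that these two outcomes are analysed by linear regression with heteroscedasticity-robust standard errors, which keep the protection against unequal variances:
- **Blood loss:** arm + pre-operative weight + height + 0 h haemoglobin.
- **Overall morphine:** arm + pain catastrophizing score + expected need for analgesics (0-100) + cohort (pilot or CMT2).

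Add four sentences. The same covariates enter the median-regression fallback. Missing baseline covariates are imputed without reference to arm, for example by the overall mean, so that no woman is dropped. Nothing measured after study drug, such as the 6-10 h haemoglobin, is used as a covariate. The unadjusted Welch result is reported as supporting.

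Pilot outcomes have already been open to a statistician by group, though not by treatment name (SAP 7.1.1). The covariates should therefore be chosen on subject-matter grounds and recorded with a date, not picked by how they perform in the pilot morphine data.

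The cost is SAP wording, an imputation rule and three degrees of freedom per model. No new data are needed and no sample size changes.

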4.2 Statistical decision rule

The primary and all secondary outcomes will be analysed with two-sided tests and confidence intervals and a statistical significance level of 5%.

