6.2.3 Uterine tone

Uterine tone will be evaluated by obstetrician in charge of the C-section at 2.5 and 5 minutes after test drug administration

A numeric rating scale ranging from 0-10 is used (0 = no effect, 7 = clinically satisfactory contraction, 10 = maximal uterus contraction). The variable will be treated as continuous in the statistical analyses.

In case of need for additional uterotonic agent(s) for adequate uterine tone, time to rescue medication will be reported as a continuous variable in minutes.

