6.2.6 Postoperative pain and side effects

Pain at rest, pain after coughing, nausea and tiredness will be registered at 4h, 10h, 24h and 48 h after administration of test drug in the CMT pilot trial..

A numeric rating scale ranging from 0-10 is used (0 = no discomfort, 10 = maximal discomfort imaginable). The variables will be treated as continuous in the statistical analyses.

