6.2.9 ECG changes

In the CMT pilot trial, the patients will be attached to a digital Holter monitor (Medilog AR4, Schiller) during the C-section to evaluate ECG changes during the first 10 minutes following administration of test drug.

The following parameters will be registered:

- Occurrence of ischemic episode (ST-segment depression of $\geq 0.1\text{mV}$). Registered as a binary variable (no ischemic episode = 0, one/more ischemic episodes = 1)
- Duration of ischemic episode. Continuous variable measured in seconds.

- Degree of ST-segment depression from baseline. Continuous variable measured in mV.
- Beat to beat analysis of QT time corrected according to Framingham. Continuous variable measured in msec.
- Occurrence of arrhythmia. Registered as a binary variable (no episodes of arrhythmia = 0, one/more episodes of arrhythmia = 1)

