7.1.2 CMT2 trial

Based on preliminary results of the CMT pilot trial, the largest difference in plasma troponin I concentration was found at 10 hours, with a mean±standard deviation change from baseline of 0.41 ± 0.79 ng/L in the carbetocin group versus a mean change of 1.78 ± 4.48 in the oxytocin group. The sample size calculation was based on 80% power to detect a between-group difference in change from baseline to 10 hours of 1.37, to be analysed using a two-sample T-test with adjustments for unequal variances. With a significance level of 5%, we will need to include 178 patients (89 in each treatment group) in the CMT2 trial. To adjust for loss of information from missing values and patient drop outs, 240 women will be enrolled. The drop-out rate after enrolment is expected to be low as the duration of the study is short.

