7.4.2 Repeated-measures continuous outcomes

The primary endpoint and all other continuous endpoints, including baseline and ≥ 1 follow-up measurements, will be analysed with linear regression models, with the follow-up measurement defined as the dependent variable and treatment group and baseline measurement defined as independent variables. Based on the fitted models, we will estimate treatment group differences in changes from baseline with 95% confidence intervals (CIs), together with a p-value for the null hypothesis of no treatment group difference. We expect at least some degree of skewness in the primary and some of the secondary endpoints, and maybe also in the residuals from the linear regression models. The amount of skewness will be assessed with histograms and descriptive statistics, such as mean, median, variance, and the skewness index. In cases where the distribution of the residuals deviates markedly from the normal distribution, or when the endpoints themselves are too skewed to use means as measures of central tendency, we will use median regression models instead of linear regression models, thus analysing between-group differences in median changes from baseline instead of mean changes from baseline. Standard errors and CIs in the median regression models will be obtained via bootstrapping with 100 replications.

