7.4.4 Categorical outcomes

Binary outcomes will be analysed with Fisher mid-P tests and Newcombe hybrid score confidence intervals for the difference between probabilities.

Ordered categorical outcomes will be analysed with score tests for effect in a proportional odds model (the Wilcoxon-Mann-Whitney test).

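### Median regression is a poor fallback for heavily tied scores: if the 0-10 uterine tone score is sent to it, the test is often miscalibrated and can lose much of its power

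*SAP*

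**What the plan says.** SAP 6.2.3 has the obstetrician score uterine tone from 0 to 10 at 2.5 and 5 minutes, with no baseline, and adds: "The variable will be treated as continuous in the statistical analyses". SAP 7.4.2 needs a baseline value, so it does not fit tone. That leaves SAP 7.4.3, applied at each time point. Its default is the Welch t-test, with an exception: "In situations where the distribution of the variable is difficult to assess or deemed to be highly skewed, median regression models will be used".

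SAP 7.4.2 has the same exception for outcomes with a baseline ("we will use median regression models instead of linear regression models"), expects some secondary endpoints to be skewed, and sets 100 bootstrap replications for standard errors and intervals. SAP 7.4.3 does not repeat the bootstrap.

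Three other provisions matter:

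- **Pain, nausea and tiredness (SAP 6.2.6).** These are also 0-10 scores treated as continuous, taken at 4, 10, 24 and 48 hours. SAP 7.4.5 sends continuous variables with more than two time points to linear mixed models and cites 7.4.2, which describes no mixed model.
- **Ischaemia (SAP 6.2.9).** "Duration of ischemic episode. Continuous variable measured in seconds". No value is given for women without an episode. Occurrence of an episode is a separate binary outcome. SAP 2.3 confines ECG analysis to the pilot.
- **Rank test (SAP 7.4.4).** "Ordered categorical outcomes will be analysed with score tests for effect in a proportional odds model (the Wilcoxon-Mann-Whitney test". It is planned for ordered categorical outcomes only. No exception is made for tied or zero-heavy variables labelled continuous.

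**The concern.** A sample median of whole-number scores can only take whole or half values. If the common median sits well inside one score, both arms usually share it. The estimated difference is then 0, and the bootstrap standard error may be 0 as well, even when the distributions differ. If the median lies on the boundary between two scores, chance alone can move one arm's median by a full point. Which case applies depends on where the scores happen to centre, not on the drugs.

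Tone is a secondary endpoint of the main trial, tested two-sided at 5% under SAP 4.2. An analyst who follows the fallback could report a tone difference that is not there, or miss one that is.

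**Working it through.** **1. The plan's own figure.** The only stated power calculation is for troponin I (SAP 7.1.2): "80% power to detect a between-group difference in change from baseline to 10 hours of 1.37", SDs 0.79 and 4.48, two-sided 5%. The normal approximation gives n per arm = (1.96 + 0.84)² × (0.79² + 4.48²) / 1.37² = 86.5. With the noncentral t and Satterthwaite degrees of freedom, power is 79.8% at 88 and 80.3% at 89 per arm. So 89 per arm (178) is reproduced. No power or error rate is stated for the outcomes discussed here.

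**2. Inputs.** From the documents: 240 women at 1:1, so 120 per arm; a 0-10 score; two-sided 5%; 100 bootstrap replications. Assumed: the score distributions, and 107 per arm in some runs (a loss of 1 − 107/120 = 11%).

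**3. Mechanism, 120 per arm.** Take the lower median, the 60th ordered value.

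- Half of all scores at 7 or below, no true difference: an arm's median is at most 7 with probability P(Bin(120, 0.5) ≥ 60) = 0.536. The two medians then fall on different sides of the boundary in 2 × 0.536 × 0.464 = 50% of trials.
- 40% at 7 or below in one arm, odds ratio 2 towards higher scores: the odds go from 0.40/0.60 = 0.667 to 0.333, so 25% are at 7 or below in the other arm. Neither arm has half its scores at 7 or below, so this shift at the cut-point does not move the median across it.

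**4. Simulation of tone, 120 per arm.** Left-skewed scores (10.5 minus a gamma variable, rounded, limited to 0-10), odds ratio 2 for power, 400 runs per cell. Test statistic: difference in medians divided by its bootstrap SE. A non-zero difference with SE 0 was counted as a rejection, which favours median regression. Cells show type I error / power of median regression, then Wilcoxon-Mann-Whitney power in brackets, all in %.

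| Median before rounding | SD 1.0 | SD 1.5 | SD 2.0 |
|---|---|---|---|
| 7.0 | 0.0 / 17.0 (83.0) | 0.7 / 61.0 (88.0) | 1.5 / 69.0 (83.0) |
| 7.25 | 1.0 / 82.3 (84.0) | 4.0 / 85.5 (84.8) | 4.8 / 79.7 (84.5) |
| 7.5 | 14.7 / 49.2 (80.5) | 10.5 / 46.5 (83.0) | 15.0 / 41.7 (87.0) |
| 7.75 | 0.7 / 1.0 (82.5) | 7.0 / 5.8 (84.8) | 7.2 / 18.2 (84.5) |
| 8.0 | 0.0 / 9.8 (83.5) | 0.0 / 52.2 (85.3) | 1.8 / 64.7 (84.0) |

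Wilcoxon-Mann-Whitney type I error was 2.8-6.2%. Median regression was outside 3-7% in 12 of 15 cells: eight at 0-1.8%, three at 10.5-15.0%, one at 7.2%. The simulation SE at 5% is √(0.05 × 0.95/400) = 1.1 points, so the 7.2% is borderline and the other eleven are clear. Power was 1-18% in five cells, 42-65% in six and 69-86% in four. Two cells (7.25 with SD 1.5 or 2.0) show no material problem.

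**5. Tone, 107 per arm.** With clear left skew (skewness −0.9 to −1.3), type I error was 4-11%. Power was 8-32%, against 79-81% for Wilcoxon-Mann-Whitney and 71-78% for Welch. With a nearly symmetric score and a half-point shift, power was 35-49% against 66-72% for Wilcoxon-Mann-Whitney.

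**6. Other outcomes, if the fallback reaches them.**

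- Ischaemia duration, 20 per arm, 0 for no episode: type I error 0-0.3% at episode rates of 10-30%, and 5-6% at 50%. Power was 1-2% against 60% for Wilcoxon-Mann-Whitney (episode rates 10% v 40%), and 25-32% against 70% (20% v 60%).
- Nausea, 40 per arm, odds ratio 2: power 3-5% against 32% with 70% zeros, but 30-32% against 37% with 55% zeros.

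**7. Control.** For a truly continuous log-normal outcome, median regression had 4-5% type I error and power of 70-71% against 89%. Ties and zeros, not skewness alone, therefore cause the failure.

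**The case against.** The fallback is conditional. Welch is the default, and it held 4-6% type I error on the 0-10 scores. A nearly symmetric tone score (a rounded normal with SD 1.4 centred on 7.0 to 7.5, skewness −0.08 to −0.17) would not clearly trigger the switch. On those data Welch had 4.9-5.2% error and 71-72% power for a half-point shift. This stands: the default is sound and the defect lies in the fallback. It does not remove the point, because clearly left-skewed tone also fails, and because the other trigger, a distribution that is hard to assess, has no threshold.

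A reader might go further in three ways that the documents do not support:

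- **That pain, nausea and tiredness are certainly affected.** SAP 7.4.5 points outcomes with more than two time points to mixed models. Because it cites a section without one, the route is unclear, but the fallback is not established for them.
- **That ischaemia measures as a class are affected.** Occurrence has its own Fisher mid-P test, so a difference in episode rate would still be tested. ST depression is measured in mV and need not be zero-heavy. Duration is zero-heavy only under a coding that the SAP does not state. All ECG data are pilot only.
- **That the fallback always loses nearly all power.** The loss ran from none to near-total, depending on distributions that the documents do not give.

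**Conclusion.** The point holds in a limited form. For uterine tone, the clear main-trial case, the fallback often gives a miscalibrated test and can lose much of its power. With 107-120 per arm, type I error was about 0-15%. Power ran from about 1% to no loss, where Wilcoxon-Mann-Whitney had about 66-88%. Duration of ischaemia shares the problem if women without an episode are coded 0. The 0-10 pain, nausea and tiredness scores share it only if they are analysed under the fallback.

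This rests on assumed score distributions, on reading tone as a single-time-point outcome at each assessment, and on the bootstrap of SAP 7.4.2 also applying in 7.4.3. The mechanism depends on none of the particular distributions; the size does. These are secondary outcomes. The primary outcome and the sample size of 178 are untouched.

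**What to change.** In SAP 7.4.3, and in 7.4.2 where it applies:

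- Exclude the 0-10 scores and zero-heavy durations from the median-regression fallback.
- Test them with the Wilcoxon-Mann-Whitney test already in SAP 7.4.4, and report the mean difference with its Welch 95% CI.
- Keep median regression only for outcomes without heavy ties.

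In SAP 6.2.9, state that duration of ischaemia is 0 for women without an episode. Keep ST depth as measured in mV: setting it to 0 for women without an episode would discard depression below the 0.1 mV threshold that was actually recorded.

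The cost is a few sentences, with no new data and no new method. The one loss is that a median difference is no longer the main estimate for these outcomes; it can still be given as description.
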